4.0 Initial Screening Questions

Updated January 2019 - Revised Common Rule (January 2018) Compliant - v92

4.1 * PROJECT SUMMARY: (REQUIRED) Give a brief overview of this project (250 words or less). Tell us what this study is about, who is being studied, and what it aims to achieve. If you have an NIH Abstract, paste it here (Click on the orange question mark to the right for more detailed instructions):

The aim of the present study is to test the effects of a digital meditation intervention in a sample of high stress UCSF employees. We propose to randomize 1000 UCSF employees to 8-weeks of either a digital mindfulness intervention (using the commerically available application Headspace) or a waitlist control condition. Measurement time points include baseline, week 4, week 8 (post intervention), and 4-month follow up period. Among participants who are randomized to the digital meditation intervention, they will also take part in a 1-year follow up. Our primary outcomes will be reductions in global levels of perceived stress and job strain. Secondary outcomes include improvements in mindfulness, symptoms of anxiety and depression, health behaviors, including sleep, physical activity, and eating behavior, and health care utilization.

Within this larger study, we will also conduct a smaller more focused substudy in which we will recruit_over weight and obese participants (BMI => 25). This study will include all of the measures obtained in the larger, main study but also expand to include physiological assessments, personal fitness and sleep metrics, and measures of daily mood data. The physiological assessments will take place at baseline and week 8, and the fitness, sleep, and mood data will be gathered for seven consecutive days at baseline and week 7. All other measurement time points are similar to those of the main study. For this substudy, we will recruit 150 additional UCSF employees, who will be randomly assigned to one of four conditions: digital meditation, a healthy eating intervention, digital meditation+healthy eating intervention, or a waitlist control condition. If participants are assigned to either of the Healthy Eating conditions, in addition to the above-mentioned assessments, they will participate in one 30- to 60-minute counseling session

centered around healthy eating behaviors such as decreasing sugar intake or the frequency of stress-related eating, and three 10-minute booster phone calls at week 1, week 4, and week 8.	
4.2 * HUD DEVICE: (REQUIRED) Does this application involve a Humanitarian Use Device (HUD):	
 No Yes, and it includes a research component Yes, and it involves clinical care ONLY 	
4.3 * TYPE OF RESEARCH: (REQUIRED) Select the option that best fits your project (Click the orange question mark to the right for definitions and guidance):	
 Biomedical research (including medical records review, biospecimen collection and/or use, other healthcare or health outcomes related activities, research database, biospecimen bank, or recruitment registry) Social, behavioral, educational, and/or public policy research Hybrid - includes aspects of BOTH types of research (check this option if your research is mainly social /behavioral but also involves specimen collection or blood draws to look at biological measures) 	
4.4 * SUBJECT CONTACT: (REQUIRED) Does this study involve ANY contact or interactions with participants:	
 Yes (including phone, email or web contact) No (limited to medical records review, biological specimen analysis, and/or data analysis) 	
4.5 * RISK LEVEL: (REQUIRED) What is your estimation of the risk level, including all screening procedures and study activities:	
Minimal risk Greater than minimal risk	
4.6 * REVIEW LEVEL: (REQUIRED) Requested review level (Click on the orange question mark to the right for definitions and guidance):	
C Full Committee	
Expedited Exempt	
4.7 * EXPEDITED REVIEW CATEGORIES: (REQUIRED) If you think this study qualifies for expedited review, select the regulatory categories that the research falls under: (check all that apply)	
 □ Category 1: A very limited number of studies of approved drugs and devices ☑ Category 2: Blood sampling □ Category 3: Noninvasive specimen collection (e.g. buccal swabs, urine, hair and nail clippings, etc.) □ Category 4: Noninvasive clinical procedures (e.g. physical sensors such as pulse oximeters, MRI, EKG, EEG, ultrasound, moderate exercise testing, etc.) ☑ Category 5: Research involving materials (data, documents, records, or specimens) that were previously collected for either nonresearch or research purposes □ Category 6: Use of recordings (voice, video, digital or image) ☑ Category 7: Low risk behavioral research or research employing survey, interview, oral history, focus group, program evaluation, human factors evaluation, or quality assurance methodologies 	

- * Does the collection of blood samples meet requirements outlined by HHS Office for Human Research Protections for **Expedited Review Research Category 2**: (REQUIRED)
 - For healthy, nonpregnant adults who weigh at least 110 pounds the amounts drawn may not exceed 550 ml in an 8 week period and collection may not occur more frequently than 2 times per week;
 - From other adults and children, considering the age, weight, and health of the subjects, the collection procedure, the amount of blood to be collected, and the frequency with which it will be collected, the amount drawn may not exceed the lesser of 50 ml or 3 ml per kg in an 8 week period and collection may not occur more frequently than 2 times per week

α		\sim	
\odot	Yes	- 50	Nο

4.9 * DATA/SPECIMEN ANALYSIS ONLY: (REQUIRED) Does this study ONLY involve records review and /or biospecimen analysis (do not check 'Yes' if this is a registry, research or recruitment database, or biospecimen repository):

\circ	Yes	(O)	Nο
*	1 5	W.C.F	140

4.10 * CLINICAL TRIAL: (REQUIRED)

Is this a clinical trial:

According to The World Health Organization (WHO) and the International Committee of Medical Journal Editors (ICMJE) a clinical trial is:

 Any research study that prospectively assigns human participants or groups of humans to one or more health-related interventions to evaluate the effects on health outcomes.

ICMJE requires registration of a clinical trial in a public database (such as ClinicalTrials.gov) prior to enrollment, for eventual publication of results in member biomedical journals.

Guidance: Public Law 110-85 requires that all investigators who perform an applicable clinical trial must ensure that the trial is registered on a government web site called **ClinicalTrials.gov**.

The FDA requires registration for 'applicable clinical trials,' defined as follows:

- For any trials of drugs and biologics: controlled clinical investigations, other than Phase 1 investigations, of a product subject to FDA regulation.
- For trials of biomedical devices: controlled trials with health outcomes of devices subject to FDA regulation, other than small feasibility studies, and pediatric post-market surveillance.

For additional information on the **ClinicalTrials.gov** registration process at UCSF and the definition of a clinical trial for purposes of registration, visit the **ClinicalTrials.gov section of the UCSF Clinical Research Resource HUB**.

Clinical Trial Registration - 'NCT' number for this trial:	
NCT03527303	
4.11 * CLINICAL TRIAL PHASE: (REQUIRED) Check the applicable phase(s):	
 Phase 0 Phase 1 Phase 1/2 Phase 2 Phase 2/3 ✓ Phase 3 Phase 4 Not Applicable 	
4.12 * INVESTIGATOR-INITIATED: (REQUIRED) Is this an investigator-initiated study:	
4.13 * CANCER: (REQUIRED) Does this study involve cancer (e.g., the study involves patients with or at risk for cancer, including behavioral research, epidemiological research, public policy research analysis, and chart reviews):	
O Yes 💿 No	
4.14 * RADIATION EXPOSURE: (REQUIRED) Does your protocol involve any radiation exposure to possible /subjects EITHER from standard care OR for research purposes (e.g., x-rays, CT-scans, DEXA, guided biopsy, radiation therapy, or nuclear medicine including PET, MUGA or bone scans):	
O Yes ⊙ No	
4.15 SCIENTIFIC REVIEW: If this study has undergone scientific or scholarly review, please indicate which entity performed the review (check all that apply):	:e
 □ Cancer Center Protocol Review Committee (PRC) (Full approval is required prior to final IRB approval for cancer-related protocols.) □ CTSI Clinical Research Services (CRS) Advisory Committee □ CTSI Consultation Services □ Departmental scientific review ☑ Other: 	
* Specify Other: (REQUIRED) UCSF Healthy Campus Network	
4.16 * STEM CELLS: (REQUIRED) Does this study involve human stem cells_(including iPS cells and stem cells), gametes or embryos:	adult
 No Yes, and requires IRB and GESCR review Yes, and requires GESCR review, but NOT IRB review 	

regi		S: (REQUIRED) Do you tner and/or depender				
O Yes (• No					
0 Fı	ınding					
		EQUIRED) Is this stud entract, OR has it recei				
Yes (• No					
	DINVOLVEMENT: Is UIRED)	this project linked in	any way to the	Departm	ent of Defe	ense (DoD)
Yes (⊙ No					
		ponsors and provide t		ails. If fu	nding come	es from a
xterna	al Sponsors:					
View Details	Sponsor Name	Sponsor Type	Awardee Institution	Contract Type:	UCSF RAS "P number" or eProposal number	UCSF RAS System Award Number ("A" + 6 digits)
	Headspace, Inc	04	UCSF	Contract	P0528111	A130873
Sponsor	Name:	Headspace, Inc				
Sponsor	Type:	04				
ponsor	Role:	Funding				
irant/C	ontract Number:	N/A				
wardee	e Institution:	UCSF				
s Instit Iolder:	ution the Primary Gran	Yes				
Contract	Туре:	Contract				
	AS "P number" or al number:	P0528111				
	AS System Award Num digits):	her A130873				
	umber for Studies Not thru UCSF:					
Grant Ti	tle:	Impact of 8 weeks				neous
PI Name (If PI is on the s	not the same as identif	ied				
Significa	nt Discrepancy:					

Other Funding Sources and Unfunded Research - Gift, Program, Departmental or other Internal Funding (check all that apply): Funded by gift (specify source below) Funded by UCSF or UC-wide program (specify source below) Specific departmental funding (specify source below) Unfunded (miscellaneous departmental funding) Unfunded student project * Identify the gift, program, departmental, or other internal funding source:	
(REQUIRED) UCOP funded Healthy Campus Network	

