Sub-study: If a participant meets the eligibility requirements for the sub-study, he or she will receive a message offering him/her the opportunity to participate. After reviewing the procedures and learning more about the procedures, a participant will have the option to join this study. If they decline participation, they will still have the opportunity to participate in the main study. If interested in the sub-study, they will be routed into a group for sub-study participants and will expect to hear from study staff to schedule an in person visit.

Clinic-visit (sub-study only): Participants interested in joining the sub-study will be contacted by a study staff member, who will guide them through the procedures and answer any questions that arise. Participants will then be scheduled for their first in-person clinic visit. The staff member will review the details of the visit, such as how to prepare and where to go.

The clinic visit assessment will consist of the following activities:

Read and sign consent form

- Height/Weight measurement to calculate BMI (confirm eligibility)
- Blood Pressure collection
- Blood Spot collection
- Waist to Hip Ratio collection
- Instruction on Morning and Nightly Diary procedures
- Orientation on Fitbit procedures

Baseline Questionnaire Battery (main study). This battery will be hosted by Qualtrics and all data will be secure. As part of this battery, participants will complete questionnaires to assess stress/distress symptoms as well the domain areas of mindfulness, health behaviors, physical health and work impact. Once completed, participants will be randomized to one of two groups: digital meditation group (Headspace) or waitlist control.

Baseline Questionnaire (Sub-study): The baseline questionnaire will be sent out to participants shortly after their visit, to complete on their own. Domain areas will be similar to the main study, with the addition of several health and eating behavior components.

Fitbit device (sub-study only): During the week prior to randomization and week 7 of the intervention period, participants will be asked to wear a Fitbit watch 24-hours per day. The Fitbit watch tracks information such as physical activity, sleep, heart rate and movement. Participants are asked to wear it at all times possible, with the exception of charging, cleaning, and syncing their device.

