Midpoint Questionnaire Battery (week 4). This battery will be hosted by Qualtrics and all data will be secure. An email link to this battery will be sent at week 4 for all study participants. This battery will be an abbreviated version of questionnaires completed at baseline, including stress/distress symptoms as well the domain areas of mindfulness, work impact, and for the sub-study, will include the domain of eating behaviors.

Post-intervention Questionnaire Battery (week 8). This battery will be hosted by Qualtrics and all data will be secure. This battery will serve as the post-intervention assessment and will be comprised of the same questionnaires included at the baseline assessment. Additionally, participants will be asked how often they have participated in a sitting meditation in the past 8 weeks. This battery will be made available to all participants via an email link.

Follow-up Questionnaire Battery (4-month follow-up (i.e., 2-months from end of intervention)). Participant s will receive a brief questionnaire battery similar to the midpoint assessment including measures of stress /distress symptoms as well the domain areas of mindfulness and work impact and health care utilization, and for the sub-study, will include the domain of eating behaviors.

Follow-up Questionnaire Battery (1-year follow-up (i.e., 10-months from end of intervention)). Participants who were initially randomized to the digital meditation condition will complete a brief questionnaire similar to the 4-month follow-up to assess the durability of the intervention, assess domains of distress, mindfulness, and work impact as well as health care utilization. The sub-study participants will also answer questions related to eating behaviors, similar to the baseline assessment.

Medical and employment record data: We are interested in whether meditation practice may affect health care utilization, job performance, and attendance. Participants will be option of making their electronic medical record and employee data available for use in this research study. All data will be collected and stored in a secured fashion, and like all the data in this study, will be deidentified. Participants can decline this request of access and continue to participate in this study.

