Re-engagement protocol: As with any digital intervention study, attrition is common. In an effort to minimize attrition in this study, we have developed a re-engagement protocol. We will send an engagement text message to each participant starting about one week into their participation and for each subsequent week, for 7 weeks. The text message content for the intervention group will consist of gentle reminders to continue to meditate, along with tips to stay active and engaged in the study. For the waitlist control group, these weekly messages will consist of encouragements and brief reminders of participation requirements (see attached doc for specific text). If a participant does not engage after about 2 weeks, then he/she will receive a phone call from our research staff. For those participants who do not answer the phone, the study staff will leave a voicemail and a subsequent text message asking to call them back, and follow up again the next day with another text message. They only hear back from the staff in 2 weeks if they continue to refrain from the meditation app.

Sub-study: Participants will follow the same re-engagement protocol listed above, with minor modifications for the healthy eating groups.

Those in the healthy eating groups will participate in 3 separate booster phone calls (5-10 minutes) to check-in regarding progress and barriers towards healthy eating goals, and feasibility/acceptability of the brief eating intervention. Participants will receive automated text message pings approximately 3 times per week. The pings will provide reminders about mindful eating (including a link to audio sessions on cravings and mindful eating). The pings will occur during identified times of "high vulnerability" from the initial counseling session.

7.10 STANDARD CLINICAL PRACTICE: To what extent, if any, do the planned research procedures differ from the care that people would otherwise receive at this institution or the study site if not being done locally:

The standard care that participants receive will not change.

7.11 INSTRUMENTS: List all questionnaires, surveys, interview, or focus group guides that will be used for this study:

If the instruments are not complete or not available because they will be developed as part of this study, describe the basic content or include an outline and submit the final versions to the IRB with a modification for approval prior to use.

Eligibility Screening.

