Mindfulness: This will be measured using the Mindful Attention Awareness Scale (MAAS) (Brown & Ryan, 2003), which assesses the tendency to be mindful day to day (15 items).

Perceived Stress: The Perceived Stress Scale (PSS) is a gold standard measure for stress perceptions, including ratings of feeling overwhelmed, out of control, and stressed, and has been extensively validated (Cohen et al, 1988). (10 items).

Job Strain: The effort-reward imbalance scale will be used to assess job strain. It contains several subscales that measure effort, reward, and overcommitment and is used routinely in both research and occupational settings (Siegrist et al., 2004) (22 items).

Work Engagement: Work engagement will be assessed using the 9 item self-report Utrech Work Engagement Scale (Schaufeli & Bakker 2003) which uses three factors to determine the level of work engagement: vigor, dedication and absorption.

The sub-study participants will also answer the following:

Palatable Eating Motives: Coping Subscale (PEMS) (Burgess, Turan, Lokken, Morse, & Boggiano, 2014). The PEMS Coping subscale is comprised of 4 Likert-like five-choice frequency response items that probe various motives for "eating tasty food and drinks." The instructions include a list of examples of these kinds of foods and sugary drinks. The list of tasty foods was adopted from the Yale Food Addiction Scale (Gearhardt, Corbin, & Brownell, 2009) with slight modifications. The Coping motives subscale measures intentionally using palatable food to cope with negative feelings (e.g., to forget about or help with worry, depression, nervousness, a bad mood, or problems). Item response choices range from almost never /never to almost always/always. The trait form for this subscale has been validated using ecological momentary assessment, and both versions are related equally to BMI and changes in emotional eating correlate with changes in BMI over time (Boggiano, Wenger, Turan, Tatum, Morgan, et al., 2015; Boggiano, Wenger, Turan, Tatum, Sylvester, et al., 2015).

Post intervention Questionnaire (week 8):

Participants will complete all the same questionnaire included in the baseline packet, with the exception of the medical and medication checklist and Adverse Childhood Events questionnaire. They will be asked about the frequency of their sitting meditation practice in the past 8 weeks.

Follow-up Questionnaire (2-months post intervention):

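### Health care utilization is a named secondary outcome, but 7.11 lists no instrument for it, and the self-report described in 7.9 has no baseline or week-8 value for either planned model to use

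*Combined protocol and SAP*

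**What the plan says.** Section 4.1 sets the outcome: "Secondary outcomes include improvements in mindfulness, symptoms of anxiety and depression, health behaviors, including sleep, physical activity, and eating behavior, and health care utilization".

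Section 7.9 describes what each questionnaire battery covers. At baseline, "participants will complete questionnaires to assess stress/distress symptoms as well the domain areas of mindfulness, health behaviors, physical health and work impact"; utilization is not among these domains. The week-8 battery "will be comprised of the same questionnaires included at the baseline assessment". The 4-month battery adds "the domain areas of mindfulness and work impact and health care utilization". The 1-year battery also names utilization, but goes only to people first randomized to digital meditation. A separate paragraph in 7.9 on medical and employment records gives utilization as one reason for requesting the electronic record, and adds: "Participants can decline this request of access and continue to participate in this study".

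Section 7.11 answers the form's instruction to "List all questionnaires, surveys, interview, or focus group guides that will be used for this study". It gives lists for screening, baseline, week 4, week 8, 4 months and 1 year. For week 8 it says "Participants will complete all the same questionnaire included in the baseline packet", apart from the medical and medication checklist and the childhood-adversity questionnaire. None of the lists includes a utilization measure.

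On analysis, 7.13 plans linear mixed models with two times (t1 and t2) and group. The SAP plans ANCOVA of each 8-week outcome across the four sub-study arms, adjusted for that measure's baseline value.

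**The concern.** A secondary outcome needs a measure, a time point and an analysis that fits both. For utilization the two sections that should supply the measure disagree. If the surveys are programmed from 7.11, utilization is not asked at all and only record data remain, for those who agree to release them. If they are programmed from 7.9, there is one controlled self-report value, collected about two months after the intervention ends, with nothing to adjust it for.

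The gap is also time-sensitive. Once a participant has been randomized, a self-report baseline can no longer be collected prospectively from that person.

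**Working it through.** No figure in the plan is at issue, so the check sets the sections side by side.

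**Step 1. Where utilization is measured by questionnaire**

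| Time | Utilization item in 7.11 | Utilization named in 7.9 battery | Arms |
|---|---|---|---|
| Screening | No | No battery described | Before randomization |
| Baseline | No | No | All |
| Week 4 | No | No | All |
| Week 8 | No (repeats baseline) | No (repeats baseline) | All |
| 4 months | No | Yes | All |
| 1 year | No | Yes | Digital meditation only |

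The count is 0 of 6 lists in 7.11 and 2 of 5 batteries in 7.9. Of those two, one has a control arm and neither precedes treatment.

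**Step 2. Whether a listed item could stand in.** The nearest baseline measures in 7.11 are days of work missed, the SF-12, the somatic-complaints items and the medical/medication checklist. They cover absence, health status, symptoms, and conditions or medicines. None is described as measuring use of care.

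**Step 3. Whether the planned models can be run on the 7.9 self-report.**
- Mixed model (7.13): this needs both groups at two times. Section 7.13 does not define t1 and t2, but no choice works, because 4 months is the only time with utilization in both groups.
- ANCOVA (SAP): this needs a week-8 outcome and a baseline covariate. Self-reported utilization has neither.

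**Step 4. Whether the medical record fills the gap.** It could reach back before randomization, so in principle it can supply a baseline. The text gives no utilization variable, look-back period, follow-up window, analysis set or model for it, and release is optional.

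**Step 5. What survives.** Under 7.9 the waitlist receives the app only after the 4-month follow-up is done or its time has passed. The randomized contrast is therefore intact at 4 months, and the arms can be compared there without a baseline.

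**The case against.** The strongest reply is that the plan has two routes to this outcome. One is the 4-month battery, given to every arm before the waitlist gets the app. The other is the medical record. For the main study, 7.9 places the release form at the consent step, before the baseline battery and randomization. Opting in would then not depend on arm, and the consenting subset remains a randomized comparison, at a cost in size and generalizability. Utilization also stands last in a summary list and appears in neither of the main-study aims.

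Most of this stands, and it limits the point. A reader might infer that an improvement cannot be measured at all. The documents do not support that: the 4-month comparison is valid without a baseline, and the record could provide one. A reader might also infer that care received elsewhere would be counted as no care and would pull the difference toward zero. No record variable or coding rule is stated, so this cannot be concluded. Nor can record coverage be sized, since the documents give neither an opt-in rate nor the share of employees treated in-house. The single-arm 1-year follow-up applies to every measure, by design, to study durability; it is not a fault peculiar to utilization.

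It might also be said that the item sits in an attachment not shown here. But 7.11 asks for all instruments, and it does list the study's own attached measures (the mind-wandering probes and the somatic-complaints items). A home-made utilization item would be expected there too.

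The reply does not remove the contradiction between 7.9 and 7.11, the absence of a self-report baseline, or the lack of an analysis that fits.

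**Conclusion.** The point holds in limited form. A named secondary outcome has no listed instrument, conflicting descriptions of when it is collected, no self-report value at baseline or week 8, and no planned model that can use the one controlled value described. The loss is baseline adjustment and within-person change and, if 7.11 governs, full-sample coverage. The validity of a 4-month between-arm comparison is not lost.

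The loss of precision cannot be quantified, because the documents give no correlation between baseline and follow-up utilization. The conclusion rests on reading 7.11 as the complete list it is asked to be, and on the model descriptions in 7.13 and the SAP as written. It concerns a secondary outcome and does not touch the primary stress and job-strain comparisons. It should be corrected, because the repair is cheap and a prospective baseline cannot be added after randomization.

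**What to change.** - Add one short utilization item set to the baseline and 4-month batteries in 7.11, for all arms, with the same wording and recall window at both (for example, counts of outpatient, emergency and mental-health visits). Bring the battery descriptions in 7.9 into line.
- State the secondary analysis as the baseline-adjusted between-arm comparison at 4 months, using a model suited to counts, such as negative binomial regression with the baseline count as covariate.
- Use record data as supportive only. Name the variable, set look-back and follow-up windows of equal length, and analyse everyone who consented to release before randomization. Do not restrict this set to people with earlier in-system visits, which would drop those who simply had no recent need of care.
- If the items are not added, remove utilization from the secondary outcomes in 4.1 or relabel it exploratory.

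The cost is about a minute of extra survey time at each of two existing online batteries and an IRB modification, with no added visits or staff. For anyone already randomized, the unadjusted 4-month comparison is what remains for self-report, provided the 4-month item is in fact asked.
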